8.2.2 Chronicity

Single occasion:	Single event with limited duration
Intermittent:	Several episodes of an event, each of limited duration
Persistent:	Event which remained indefinitely

8.2.3 Causality

Not Related	This category applies to those adverse events which, after careful consideration, are clearly due to extraneous causes (disease, environment, etc.)
Unlikely	In general, this category can be considered applicable to those adverse events which, after careful medical consideration at the time they are unrelated to the test drug. An adverse event may be considered unlikely to be related if or when (must have two of the following): 
1. It does not follow a reasonable temporal sequence from administration of the study treatment.2. It could readily have been produced by the patient's clinical state, environmental or toxic factors, or other modes of therapy administered to the patients.3. It does not follow a known pattern of response to the study treatment.4. It does not reappear or worsen when the study treatment is re-administered.
Possibly	This category applies to those adverse events for which, after careful medical consideration at the time they are evaluated, a connection with the study treatment administration appears unlikely but cannot be ruled out with certainty. An adverse event may be considered possibly related if or when (must have two of the following): 
1. It follows a reasonable temporal sequence from administration of the study treatment.2. It could not readily have been produced by the patient's clinical state, environmental or toxic factors, or other modes of therapy administered to the patients.3. It follows a known pattern of response to the study treatment.
Definitely	This category applies to those adverse events which the Investigator feels are incontrovertibly related to study treatment. An adverse event may be assigned an attribution of definitely related if or when (must have all of the following): 
1. It follows a reasonable temporal sequence from administration of the study treatment.2. It could not be reasonably explained by the known characteristics of the patient's clinical state, environmental, or toxic factors, or other modes of therapy administered to the patients.3. It disappears or decreases on cessation or reduction in dose and recurs with re-exposure to drug. (Note: this is not to be construed

as requiring re-exposure of the patient; however, a category of definitely related can only be used when a recurrence is observed.)

4. It follows a known pattern of response to the study treatment.

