5 STUDY TREATMENTS

5.1 Study Treatments Administered

[figure not shown]
Patients will receive the following three single doses in a randomised sequence at Visit 2 to Visit 4:

1. 1.5 mg RPL554
2. 6 mg RPL554
3. Placebo

All three study treatments will be administered using the inhaled route with nebulised RPL554 or placebo administered using a standard Jet nebuliser (PARI LC Sprint plus a PARI TurboBOY SX compressor unit) as described in Section 5.4.2.

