10.4.7 Safety

Safety data including safety laboratory tests, 12-lead ECG parameters, vital signs and physical examinations, will be summarised by treatment group and time point, when appropriate. For continuous variables, the change from baseline (pre-dose at each treatment visit) to each post-dose time point will also be calculated and summarised. Data will further be illustrated by shift tables (showing changes from low/normal/high) and shift plots for selected time points.

Coded adverse event terms will be presented by system organ class (SOC) and preferred term and summarised by treatment group. A summary table by treatment group with total number and number of patients with adverse events, SAEs, adverse events leading to discontinuation of study treatment, causally related adverse events and severe adverse events will be produced. Further SAEs, causally related adverse events and adverse events of each intensity will be summarised by SOC and preferred term.

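### Protocol 8.2.3 describes Possibly as an unlikely link, and its non-recurrence criterion lets one adverse event meet both Unlikely and Possibly

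*Protocol*

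**What the plan says.** Protocol 8.2.3 gives the Investigator four causality levels: Not Related, Unlikely, Possibly and Definitely. SAP 4.5.1 repeats the same four.

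- **Unlikely** needs two of four criteria: timing not reasonable, another cause could readily explain the event, no known pattern, and "It does not reappear or worsen when the study treatment is re-administered".
- **Possibly** covers events for which "a connection with the study treatment administration appears unlikely but cannot be ruled out with certainty". It needs two of three criteria: reasonable timing, no ready alternative cause, known pattern.
- **Definitely** needs all of its criteria, including "It disappears or decreases on cessation or reduction in dose and recurs with re-exposure to drug". A note says that re-exposing the patient is not being demanded, but that "a category of definitely related can only be used when a recurrence is observed".

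On dosing, Protocol 5.1 states: "Patients will receive the following three single doses in a randomised sequence at Visit 2 to Visit 4". These are 1.5 mg RPL554, 6 mg RPL554 and placebo, and the section calls all three study treatments. Protocol 5.8 blinds the Investigator to allocation.

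On reporting, Protocol 10.4.7 promises a table by treatment group in which, among other counts, "causally related adverse events and severe adverse events will be produced". SAP Table 14.3.1.3 gives causally related events by system organ class and preferred term. The protocol synopsis also plans a summary by relationship to treatment. SAP 6.4.7.1 defines causally related as Unlikely, Probably or Definitely. Probably is not on the scale, and Possibly is not in the definition.

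**The concern.** The description of Possibly and its criteria point in opposite directions. An assessor who follows the description and one who follows the criteria can record the same event differently.

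The non-recurrence criterion under Unlikely has no counterpart under Possibly, so an event can satisfy both lists, and no rule says which prevails. The criterion also refers to the study treatment, which here includes placebo. By contrast, the recurrence criterion under Definitely refers to drug. Read literally, an event seen after RPL554 and absent after placebo scores a point towards Unlikely, although that contrast favours a drug effect. A blinded Investigator cannot tell that case from absence after a second active dose.

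Tolerability and safety are a secondary objective. With 10 planned completers, one patient is 1/10 = 10 percentage points of a treatment column, so one inconsistently rated event would show.

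**Working it through.** The plan states no figure on this point. The check is a count over the criteria and over the treatment orders.

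**1. The two lists side by side (Protocol 8.2.3)**

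| Criterion | Unlikely (two of four) | Possibly (two of three) |
|---|---|---|
| Timing | not reasonable | reasonable |
| Other cause | readily explains | does not readily explain |
| Known pattern | no | yes |
| Given again | no reappearance or worsening | no counterpart |

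The first three rows are exact opposites.

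**2. Overlap.** Let f be the number of the three shared criteria that favour the drug (0 to 3). Let n = 1 if study treatment is given again and the event does not reappear or worsen, and n = 0 otherwise. Reading the threshold as at least two:

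- Possibly if f ≥ 2
- Unlikely if (3 − f) + n ≥ 2

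There are 1, 3, 3 and 1 patterns with f = 0, 1, 2 and 3.

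- n = 0: Unlikely requires f ≤ 1. That gives 4 patterns Unlikely, 4 Possibly, none both and none neither. This covers two situations (not given again; given again and recurred), so 0 of 2 × 8 = 16 combinations overlap.
- n = 1: Unlikely requires f ≤ 2. The 3 patterns with f = 2 meet both levels, and the single pattern with f = 3 meets Possibly only. So 3 of the 4 patterns that meet Possibly also meet Unlikely.

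Reading the threshold as exactly two gives the same 3 overlaps. It also leaves the f = 3 pattern meeting neither level.

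**3. What non-recurrence means in this design.** Protocol 5.7 does not list the sequences; assume all six orders are used equally. With L = 1.5 mg, H = 6 mg and P = placebo, the treatment given next after each active dose is:

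| Order | After first active dose | After second active dose |
|---|---|---|
| L H P | H | P |
| H L P | L | P |
| L P H | P | none |
| H P L | P | none |
| P L H | H | none |
| P H L | L | none |

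Of 12 active doses, 4 are followed next by the other active dose, 4 by placebo and 4 by nothing. Among the 8 followed by something, the next treatment is placebo in half and a dose differing by a factor of 6/1.5 = 4 in the other half. It is never the same dose.

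**4. Definitely.** Counting any later active dose, not only the next treatment, 6 of 12 active doses are followed by one. This half does not depend on the orders used: each completer has one earlier and one last active dose, which gives 10 of 20 for 10 completers. An event first seen at the last active dose cannot be Definitely. If all three shared criteria favour the drug (f = 3) but no recurrence is seen, only Possibly is left, under its description as unlikely.

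**5. Does the overlap move the related-event table?**

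| SAP 6.4.7.1 definition | Overlap event recorded Unlikely | Recorded Possibly | Table moves? |
|---|---|---|---|
| As written (Unlikely, Probably, Definitely) | counted | not counted | yes |
| Probably is a slip for Possibly | counted | counted | no |
| Corrected to Possibly and Definitely | not counted | counted | yes |

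**The case against.** Several points on the other side stand.

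- A reader might infer that the scale cannot separate its levels. The documents do not support that. On the three shared criteria Unlikely and Possibly split cleanly, and the overlap comes only from the non-recurrence criterion.
- A reader might infer that single doses rarely allow a recurrence. The crossover re-exposes every completer to RPL554 once. The documents give no recurrence rate, so it cannot be said that Definitely will be nearly empty.
- Requiring recurrence for a level reserved for incontrovertible cases is a defensible strict threshold.
- The half in step 4 counts doses, not events. With balanced orders and no period effect, the share of first appearances at the last active dose is at most half, because an event that would occur at both doses appears first at the earlier one.
- The 3 of 4 counts logical patterns, not expected events.
- The criteria are permissive, and an event rated before the next visit, at least 3 days later, has n = 0 and no overlap. This helps only in part. The recurrence and non-recurrence criteria both presuppose a rating made or revisited after a later dose, and 8.2.3 does not say when a rating is final.
- A reader might infer that the relatedness tables are unreliable. If Probably in SAP 6.4.7.1 is a slip for Possibly, Unlikely and Possibly are pooled and the overlap moves nothing there. SAP 8.1 lists no table by causality level. The all-event tables by treatment, including placebo, do not use causality at all.

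**Conclusion.** The point holds in a limited form. The description of Possibly contradicts its criteria. The non-recurrence criterion makes 3 of the 4 Possibly patterns also Unlikely when the event does not recur, and none otherwise. That criterion is poorly suited to a crossover in which the next treatment is placebo or a different dose.

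The effect on the tables is conditional. It is nil if SAP 6.4.7.1 is meant to pool Unlikely, Possibly and Definitely. It is present if the definition is applied as written or corrected to Possibly and Definitely. How many events would be affected cannot be derived from the documents.

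The bar on Definitely for events first seen at the last active dose is a limit on interpretation, not an error.

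The conclusion assumes that two criteria means at least two (exactly two does not remove the overlap) and, for the placebo count in step 3 only, that the six orders are used equally. The correction is worth making because it repairs what the assessor records, which no later SAP edit can restore.

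**What to change.** 1. In Protocol 8.2.3, describe Possibly as a reasonable possibility of a causal link and remove the statement that the link appears unlikely.
2. Drop the non-recurrence criterion under Unlikely, or qualify it so that absence after placebo or after a different dose does not count.
3. State that an event meeting both levels is recorded at the higher one.
4. In SAP 6.4.7.1, define causally related using only levels on the four-level scale. Do this together with item 3: under the definition as written, recording the higher level would take events out of the related table.
5. In the study report, note that an event first seen at a patient's last active dose could not be rated Definitely, so few such ratings are not evidence of safety. Relaxing the recurrence requirement is optional.

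The cost is protocol wording, a CRF completion note and one SAP sentence. No new data are needed and the four levels stay. A few more events may be rated Possibly.

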8.2.4 Action and Outcome

- Action taken with study treatment (none, study treatment stopped, study treatment temporarily interrupted)
- Other actions (none, concomitant medication, study discontinuation, hospitalisation, other)
- The outcome and date of outcome according to the following definitions:
 - Recovered or resolved (adverse event disappeared)
 - Recovering or resolving (patient is recovering)
 - Not recovered or not resolved (adverse event remains without signs of improvement)
 - Recovered or resolved with sequelae (adverse event has resulted in permanent disability or incapacity)
 - Fatal
 - Unknown (only applicable if patient has been lost to follow-up)
- Seriousness (yes or no)

8.3 Reporting Procedure for SAEs

The Investigator must report all SAEs to the Sponsor by telephone and in writing using the Sponsor's reporting form and emailed (email address included on Page 2) to as soon as practical, but at least within 24 hours of awareness. Any fatal SAEs notified in the 30 day period after the last dose of study treatment must also be reported

SUSARs will be determined by the Sponsor's Medical Monitor.

SAEs will be reported to the ethics committee and regulatory authority according to local requirements.

All adverse events will be followed until they have abated, or until a stable situation has been reached. Depending on the event, follow up may require additional tests or medical procedures as indicated, and/or referral to the patient's general physician or a medical specialist.

It is the responsibility of the Sponsor and of the Investigator to ensure that any necessary additional therapeutic measures and follow-up procedures are performed.

8.4 Management of Pregnancies

Should a female patient become pregnant during the study or in the 30 days after the end of the study they must inform the Investigator immediately. The Investigator will report this information to the Sponsor within 7 days of awareness. The Investigator will make all reasonable efforts to ascertain the progress and outcome of the pregnancy. If the outcome meets the criteria for immediate classification of a SAE (e.g. spontaneous or therapeutic

abortion, stillbirth, neonatal death, congenital anomaly, birth defect), the Investigator must follow the procedure for reporting SAEs.

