3.4 Definition of the End of the Study

The end of the study is defined as the date of the last end of study visit of the last patient in the study.

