4.1 Inclusion Criteria

1. Sign an informed consent document indicating they understand the purpose of and procedures required for the study and are willing to participate in the study.
2. Male or female aged ≥ 18 years at the time of informed consent. Females of childbearing potential must have been using a consistent and reliable form of contraception (see Appendix 1) from the last menses before the first study treatment administration, and must commit to continue to do so during the study and for 3 months after the last dose of study treatment.
3. Have a 12-lead ECG recording at screening (Visit 1) and Visit 2 pre-dose showing the following:
 - Heart rate between 50 and 100 beats per minute
 - QT interval corrected for heart rate using Fridericia's formula (QTcF) interval ≤ 450 msec
 - QRS interval ≤ 120 msec
 - PR interval ≤ 200 msec
 - No clinically significant abnormality including morphology (e.g. left bundle branch block, atrioventricular nodal dysfunction, ST segment abnormalities)
4. Capable of complying with all study restrictions and procedures including ability to use the study nebuliser correctly.
5. Body mass index (BMI) between 18 and 30 kg/m^2 (inclusive) with a minimum weight of 40 kg.
6. Patients with a genetic diagnosis of CF.
7. Spirometry at screening demonstrating an $\text{FEV}_1 \geq 40\%$ and $\leq 80\%$ of predicted normal.
8. Capable of withdrawing from long acting bronchodilators for 48 hours prior to study visits, and short acting bronchodilators for 8 hours prior to study visits.
9. Clinically stable CF in the 2 weeks prior to randomisation (Visit 2).

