4.3 Removal of Patients from Therapy or Assessment

Investigators have the authority to ask for the withdrawal of a patient at any time for medical or non-compliance reasons. Should the Investigator decide it is necessary to withdraw any patient for specific reasons, this should be recorded in writing and discussed with the patient in question. Such reasons for withdrawal are expected to be medical or related to lack of co-operation by the patient.

If a patient withdraws following randomisation, every attempt should be made to contact the patient to determine the reason for withdrawal and to complete the recording of any available pharmacodynamic data and all adverse event data. If a patient agreed to enter the study and signed a consent form but withdrew from the study, or was withdrawn from the study, without receiving any study treatment, no further follow-up is necessary.

End of study visits will occur 3 to 10 days after the last dose of study treatment. All withdrawn patients will follow this routine unless it is considered by the Investigator that they require greater medical supervision and/or investigations and in which case an unscheduled visit prior to and in addition to the scheduled follow up visit may be performed.

If a patient decides to withdraw voluntarily, or is withdrawn by the Investigator responsible at any time, the reasons for withdrawal and results of all relevant tests will be recorded in the case report form (CRF). Patients who withdraw may be replaced.

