7.4.2 Laboratory Safety Assessments

All female patients will have a urine pregnancy test at screening (Visit 1), pre-dose at Visit 2 to Visit 4 and at the end of study visit (Visit 5) according to the study centre's standard operating procedures (SOPs).

All other laboratory safety assessments will be performed at each study centre's local laboratory. Samples will be handled and analysed according to the study centre and local laboratory standard procedures.

Monovette-S® (Sarstedt) tubes will be used to collect safety laboratory blood samples. Two samples will be collected at each timepoint, one sample for haematology using a 2.6 mL ethylenediaminetetraacetic acid (EDTA) whole blood collection tube and one 4.7 mL sample for biochemistry using a serum tube. A midstream urine sample will also be collected in a sterile container.

Samples will be taken at screening (Visit 1) and end of study visit (Visit 5) and analysed for:

Haematology: haemoglobin, haematocrit, total white cell count, leukocyte differential count and platelet count

Biochemistry: creatinine, total bilirubin, alkaline phosphatase, alanine transaminase, gamma-GT, potassium, sodium, urea

Urinalysis: leukocytes, blood, ketones, bilirubin, urobilinogen, protein and glucose using a dipstick. In the event of an abnormal dipstick urinalysis result, microscopic urinalysis may be conducted.

In addition, unscheduled and/or repeat testing may be performed at the discretion of the Investigator. Laboratory results will be provided to the Investigator for each patient and each visit. The Investigator should assign whether each abnormal result is not clinically significant or a clinically significant.

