8.2 Recording and Assessing Adverse Events

All adverse events, whether reported spontaneously by the patient, in response to open questioning on treatment days or observed by the Investigator or his/her staff, will be recorded from informed consent until the end of study visit (Visit 5).

The start and stop time will be recorded and adverse events will be assessed by the Investigator for the following:

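### The duty to report a pregnancy runs from a trial-wide date, while the contraception commitment runs from each woman's own last dose, so late finishers have part of that period without required notification

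*Protocol*

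**What the plan says.** On contraception, Protocol section 4.1, criterion 2, says that females of childbearing potential "must commit to continue to do so during the study and for 3 months after the last dose of study treatment". Protocol Appendix 1 and SAP Appendix 1 repeat this. The clock starts at the individual woman's last dose.

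On reporting, Protocol section 8.4 begins "Should a female patient become pregnant during the study or in the 30 days after the end of the study", and in that case requires her to tell the Investigator at once. The Investigator then passes the report to the Sponsor within 7 days and tries to follow the pregnancy to its outcome. Certain outcomes are handled as serious adverse events. All of this starts with the patient's notification.

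On the anchor, Protocol section 3.4 states: "The end of the study is defined as the date of the last end of study visit of the last patient in the study". This is one date for the whole trial. The individual patient's final attendance is Visit 5, and section 4.3 gives its timing: "End of study visits will occur 3 to 10 days after the last dose of study treatment".

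Other follow-up does not extend further. Section 7.4.2 schedules the last urine pregnancy test at Visit 5, and section 8.2 stops adverse event recording there. Section 8.3 has the only other window after the study: "Any fatal SAEs notified in the 30 day period after the last dose of study treatment must also be reported". It covers fatal events only, and it is counted from the last dose.

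**The concern.** The two windows differ in length and in starting point. One runs three months from a woman's own last dose. The other runs 30 days from a date set by whoever finishes last. Two women with identical exposure can therefore have different reporting duties purely because of enrolment order. The completion date is also hard to predict: section 4.3.4 replaces patients who do not complete, and section 5.9.1 allows washouts beyond 14 days after antibiotic treatment.

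What is at stake is completeness of pregnancy follow-up. A woman who conceives while still under the contraception commitment, but after the 8.4 window has closed, has no duty to tell anyone. The chain from Investigator to Sponsor to outcome may then never start.

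**Working it through.** The plan states no figure of its own here, so the check is date arithmetic.

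**Inputs**
- *d*, days from a woman's last dose to her own Visit 5: 3 to 10 (Protocol 4.3).
- Notification period after study end: 30 days (Protocol 8.4).
- *L*, days from her Visit 5 to the last patient's Visit 5, which is study end under section 3.4. The documents do not give it, so it is varied.
- *M*, the three-month contraception period in days: 89 to 92 calendar days depending on the months involved, with 90 as the central value (assumption).

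**Formulas**
- Notification cover after last dose = d + L + 30.
- Uncovered part of the contraception period = max(0, M − (d + L + 30)).

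**Last patient to finish (L = 0)**
- Cover: 3 + 30 = 33 days to 10 + 30 = 40 days.
- Gap with M = 90: 90 − 40 = 50 to 90 − 33 = 57 days.
- Gap over the full range of M: 89 − 40 = 49 to 92 − 33 = 59 days.
- As a share of the period: 49/89 = 55% to 59/92 = 64%.

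**Earlier finishers**

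| L (days before the last patient's Visit 5) | Gap in days, M = 90 | Gap in days, M = 89 to 92 |
|---|---|---|
| 0 | 50 to 57 | 49 to 59 |
| 14 | 36 to 43 | 35 to 45 |
| 28 | 22 to 29 | 21 to 31 |
| 42 | 8 to 15 | 7 to 17 |
| 50 | 0 to 7 | 0 to 9 |
| 57 | 0 | 0 to 2 |
| 60 | 0 | 0 |

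The gap closes once L reaches M − d − 30. That is 50 to 57 days for M = 90, or 49 to 59 days over the full range, roughly 7 to 8 weeks. Women who finished earlier still have a reporting window longer than the contraception period.

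**Position relative to drug elimination**
- Protocol section 3.2 takes five half-lives as the elimination time.
- The longest individual half-life it reports is 26.3 h, after multiple dosing in healthy subjects: 5 × 26.3 = 131.5 h, about 5.5 days.
- The longest after a single dose is 12.5 h: 5 × 12.5 = 62.5 h, about 2.6 days.
- The shortest reporting window closes at 33 days, about six times 5.5 days. Half-lives in CF patients are not given.

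**With the window counted from each patient's last dose and made equal to the contraception period**, the gap is M − M = 0 for every patient, whatever L is.

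**The case against.** The strongest reply is that the passages do not contradict each other. One sets how long a woman avoids pregnancy, the other which pregnancies she must report. Both can be followed at once, and nothing in the documents says the windows must match. That stands, so this is a gap in follow-up and not an impossible instruction.

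Three stronger readings are tempting, and the documents do not support them:

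- *Drug-exposed pregnancies would be missed.* On the half-lives in section 3.2, a conception in the uncovered days comes long after the stated elimination time. The protocol gives no reason for choosing three months.
- *Every female patient has a gap of about 50 days or more.* This requires reading study end in 8.4 as each patient's own Visit 5, but section 3.4 defines it at trial level. On that other reading the dependence on the last patient would also disappear, so the two claims cannot be made together.
- *Pregnancies in the gap are wholly unmonitored.* Section 8.4 does not bar a voluntary report. It is worded by when the woman becomes pregnant, so a conception inside the window that is discovered later is still notifiable. What is missing is a required report and a scheduled test.

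The numbers are also small. About 10 patients complete, and the documents give neither the number of women of childbearing potential nor the recruitment timetable, so the number affected could be zero or one.

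What survives is that each woman's duty depends on other patients' dates, and that for late finishers it stops short of the precaution period the protocol itself sets.

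**Conclusion.** The point holds as a limited safety follow-up gap. It is certain for a woman of childbearing potential who finishes last, at about 49 to 59 days. It is smaller for those finishing before her, and absent for those finishing some 7 to 8 weeks or more earlier. These figures rest on the section 3.4 definition applying in 8.4, on Visit 5 falling within its 3 to 10 day window, and on three months being 89 to 92 days. The spread of finishing dates is unknown, so the number of women affected cannot be stated. No view is taken on which duration is right. Sample size, analysis sets, endpoints and planned tests are unaffected.

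**What to change.** Reconcile Protocol sections 3.4, 4.1 (criterion 2) and 8.4 with Appendix 1. In 8.4, replace the study-end anchor with each patient's own last dose, and let the reporting window run as long as whatever contraception period the protocol retains. If that period is itself revised, update the synopsis and SAP Appendix 1 to match.

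The cost is one sentence in 8.4 and matching wording in the patient information sheet, which is not among the documents reviewed, so its present content is unknown. If the change counts as a substantial amendment, section 11.2 requires ethical and regulatory approval. No visit or test is added, because the report comes from the patient.
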